5.1. Inclusion Criteria

Patients are eligible to be included in the trial only if all the following criteria apply:

101. Able to comprehend and willing to sign an ICF and willing to comply with all trial procedures and restrictions for the duration specified in the Schedule of Activities (SoA; [Section 1.3](#)).
102. Males and females between 18 and 85 years of age, inclusive, at screening.
103. Body mass index $<35 \text{ kg/m}^2$.
104. Diagnosed with HCM per the following criteria:
 - a. Has LV hypertrophy and non-dilated LV chamber in the absence of other cardiac disease and
 - b. Has an end-diastolic LV wall thickness as measured by the echocardiography core laboratory of:
 - $\geq 15 \text{ mm}$ in one or more myocardial segments OR
 - $\geq 13 \text{ mm}$ in one or more wall segments *and* a known-disease-causing gene mutation or positive family history of HCM
105. Has resting LVOT-G $\geq 30 \text{ mmHg}$ and post-Valsalva LVOT-G $\geq 50 \text{ mmHg}$ during screening as determined by the echocardiography core laboratory
106. LVEF $\geq 60\%$ at screening as determined by the echocardiography core laboratory.
107. New York Heart Association (NYHA) Functional Class II or III at screening
108. Hemoglobin $\geq 10 \text{ g/dL}$ at screening.
109. Respiratory exchange ratio (RER) ≥ 1.05 and $p\text{VO}_2 \leq 90\%$ predicted on the screening CPET per the core laboratory.
110. Patients on beta-blockers, verapamil, diltiazem, or disopyramide should have been on a stable regimen for >6 weeks prior to randomization and anticipate remaining on the same medication regimen during the trial. Patients treated with disopyramide must also be concomitantly treated with a beta blocker and/or calcium channel blocker.

111. Male patients are eligible to participate if they agree to the following:
- a) Refrain from donating sperm during the trial plus at least 10 weeks after the last dose of IP
- AND
- b) During the trial plus 4 weeks after the last dose of IP either:
 - 1. Be abstinent from heterosexual intercourse as their preferred and usual lifestyle (abstinent on a long term and persistent basis) and agree to remain abstinent in writing
- OR
- 2. Must agree to use a male condom when his female partner is a woman of childbearing potential, and have his female partner use a highly effective method of contraception (as described in Appendix 3 [Section 10.3])

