8.2.4. New York Heart Association Functional Classification

After interviewing the patient, the investigator (or qualified designee) will record the NYHA Functional Classification in the CRF ([Criteria Committee of the New York Heart 1994](#)). The NYHA classification is as follows:

- Class I - No symptoms and no limitation in ordinary physical activity (eg, shortness of breath when walking, climbing stairs)

- Class II - Mild symptoms (eg, mild shortness of breath and/or angina) and slight limitation during ordinary activity.
- Class III - Marked limitation in activity due to symptoms, even during less-than-ordinary activity (eg, walking short distances [20-100 m]). Comfortable only at rest.
- Class IV - Severe limitations. Experiences symptoms even while at rest. Mostly bedbound patients.

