2.2.2. Secondary Endpoints

- Change in Kansas City Cardiomyopathy Questionnaire – Clinical Summary Score (KCCQ-CSS) from baseline to Week 12 and Week 24
- Proportion of patients with ≥ 1 class improvement in NYHA Functional Class from baseline to Week 12 and Week 24
- Change in post-Valsalva LVOT-G from baseline to Week 12 and Week 24
- Proportion of patients with post-Valsalva LVOT-G < 30 mmHg at Week 12 and Week 24
- Total duration of SRT eligibility during the 24-Week treatment period in patients who were SRT eligible at baseline
- Change in total workload during CPET from baseline to Week 24

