7.5. Subgroup Analyses

Subgroup analyses with relatively moderate sample size will be performed to examine the consistency of the observed treatment effect and to gain insight into the effectiveness of aficamten in subpopulations. Analyses of the primary endpoint will be conducted for the following subgroups:

- Sex (male, female)
- Age group (< 65, ≥ 65 years old)
- Baseline body mass index (<30 vs. ≥ 30)
- Baseline NYHA Class (II, III)
- Baseline KCCQ CSS (≤ median and > median)
- Baseline LVEF (≤ median and > median)
- Baseline N-terminal prohormone brain natriuretic (NT-proBNP) (≤ median and > median)

- CPET modality (treadmill, bicycle)
- Baseline pVO₂ (\leq median, $>$ median)
- Beta Blocker (use, no use)
- Baseline resting LVOT (\leq median and $>$ median)
- Sarcomeric gene mutation status (pathogenic or variant of uncertain significance, and non-disease causing or none)

Subgroup analysis will be performed by including the subgroup effect and subgroup by treatment interaction to the model. The subgroup analysis will be performed based on the imputed dataset generated for the primary analysis of the endpoint if the primary analysis is based on multiple imputation.

In addition, subgroup of IND site status (IND sites vs. non-IND sites) analysis will be performed for the primary estimand, proportion of patients with >1 NYHA functional class improvement, KCCQ CSS change from baseline, post-Valsalva LVOT-G change from baseline at Week 24 and overall adverse events summary to demonstrate compliance with relevant aspects of 21 CFR 312.120.

Analyses on the primary and secondary endpoints in patients who were SRT eligible at baseline may be explored.

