7.6. Multiple Comparisons and Multiplicity

The null hypothesis for the primary and secondary efficacy variables in the FAS will be tested in the pre-specified order using a closed testing procedure.

For preservation of the overall type I error rate at two-sided 0.05 for the primary and secondary endpoints, the closed testing procedure will be used to address multiplicity. The primary endpoint is tested first at two-sided 0.05. If the primary endpoint achieves statistical significance at two-sided alpha level of 0.05, then the secondary endpoints will be tested at two-sided 0.05, with their testing being in the sequential order of KCCQ-CSS change from baseline, proportion of patients with ≥ 1 NYHA functional class improvement, post-Valsalva LVOT-G change from baseline, and proportion of patients with post-Valsalva LVOT-G < 30 mmHg in FAS at Week 24; duration of SRT eligibility up to 24 weeks of treatment for those who were SRT eligible at baseline; KCCQ-CSS change from baseline, proportion of patients with ≥ 1 NYHA functional class improvement, post-Valsalva LVOT-G change from baseline, and proportion of patients with post-Valsalva LVOT-G < 30 mmHg in FAS at Week 12; and change from baseline to Week 24 in total workload. The testing steps are described as follows in [Table 4](#):

Table 4: Testing Steps

Step 1	The null hypothesis for the primary endpoint is that there is no treatment difference in the change from baseline to Week 24 in pVO ₂ between patients randomized to placebo and those randomized to aficamten in the FAS. The hypothesis will be tested at the two-sided significance level of 0.05. If this hypothesis is rejected, testing will proceed to Step 2; otherwise testing will stop.
Step 2	The null hypothesis for the first secondary endpoint is that there is no treatment difference in the change from baseline to Week 24 in KCCQ-CSS in the FAS. The hypotheses will be tested at the two-sided significance level of 0.05. If this hypothesis is rejected, testing will proceed to Step 3; otherwise testing will stop.
Step 3	The null hypothesis for the second secondary endpoint is that there is no treatment difference in proportion of patients with ≥ 1 NYHA functional class improvement at Week 24 in the FAS. The hypotheses will be tested at the two-sided significance level of 0.05. If this hypothesis is rejected, testing will proceed to Step 4; otherwise testing will stop.

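### SAP 7.5 sets the IND-site NYHA analysis at more than one class of improvement, while the secondary endpoint, Step 3 and Table 6 use at least one class

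*SAP*

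**What the plan says.** After its main subgroup list, SAP 7.5 adds an analysis by IND site status. It covers the primary estimand, the "proportion of patients with >1 NYHA functional class improvement", then "KCCQ CSS change from baseline, post-Valsalva LVOT-G change from baseline at Week 24", and an overall adverse event summary. The stated purpose is to show compliance with the relevant parts of 21 CFR 312.120. The SAP version history says that analyses by IND site status were added so that their scope would be consistent; it mentions no new NYHA endpoint.

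The confirmatory NYHA endpoint has a different threshold. SAP 7.6, Table 4, Step 3 tests for "no treatment difference in proportion of patients with ≥ 1 NYHA functional class improvement at Week 24 in the FAS". The same threshold of at least one class appears in SAP 2.2.2, Step 8 of Table 4, SAP 7.8, SAP 7.8.1 item 3 and SAP Table 6, and in Protocol Table 2, 9.4.1.1 and 9.4.3.

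On who can respond, Protocol 5.1 (criterion 107) admits "New York Heart Association (NYHA) Functional Class II or III at screening", and SAP 7.5 lists Classes II and III as the two baseline NYHA subgroups. Protocol 8.2.4 puts the top of the scale at "Class I - No symptoms and no limitation in ordinary physical activity".

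The Table 6 row for the ≥1 NYHA endpoint plans subgroup analyses for the variables of Section 7.5. SAP 7.8.1 item 3 gives the method: the CMH test is repeated within each subgroup level, without the randomization strata.

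**The concern.** On an integer scale, more than one class means two or more. That is a different responder from the one in the testing hierarchy, and many enrolled patients cannot meet it whatever the treatment does.

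The analysis is there to show a regulator that results hold across IND and non-IND sites. A programmer who follows SAP 7.5 literally will tabulate an endpoint that the trial does not otherwise define, and the table will not line up with the Step 3 result. A programmer who quietly uses ≥1 will produce output that departs from the signed plan. Either way, Section 7.5 and Table 6 give different instructions for what looks like the same quantity.

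**Working it through.** The plan states no figure to reproduce here. The check is an enumeration of the NYHA scale.

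Inputs:
- Scale: integer classes I to IV, with I the best (Protocol 8.2.4).
- Entry: Class II or III at screening (Protocol 5.1).
- Threshold in the IND-site item: >1 class (SAP 7.5).
- Threshold in Step 3: ≥1 class at Week 24 (SAP 7.6, Table 4).

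Improvement = baseline class − Week 24 class.

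| Baseline class | Largest possible improvement | Week 24 classes meeting ≥1 | Week 24 classes meeting >1 |
|---|---|---|---|
| II | 2 − 1 = 1 | I | none |
| III | 3 − 1 = 2 | II or I | I only |

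Two groups that can respond in Step 3 become non-responders under SAP 7.5 as written: every baseline Class II patient who reaches Class I, and every Class III patient who moves to Class II.

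Let s be the share of patients in Class III at baseline, with the rest in Class II.
- Largest possible response under ≥1: (1 − s) × 100% + s × 100% = 100%.
- Largest possible response under >1: (1 − s) × 0% + s × 100% = s.

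The documents do not give s. Under assumed values:

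| Assumed s | Ceiling under >1 | Ceiling under ≥1 |
|---|---|---|
| 10% | 10% | 100% |
| 25% | 25% | 100% |
| 50% | 50% | 100% |

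The ceiling applies to each arm and each site group, with s taken within that cell.

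Entry is judged at screening, whereas baseline under SAP 5.6 is the last measurement before the first dose, and NYHA class is recorded again on Day 1. A few patients could therefore have a baseline of Class I or IV. That would shift the ceiling slightly but would not change the result for Class II.

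SAP 7.5 does not say which endpoint the NYHA item is meant to be, so this has to be inferred. Its companions in the list are Step 1 (pVO₂), Step 2 (KCCQ-CSS change) and Step 4 (post-Valsalva gradient change), with Week 24 given at the end of the list. The item sits where Step 3 would. With no >1 class endpoint anywhere else, including the long exploratory list in SAP 2.2.3, the natural reading is that Step 3 was intended.

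**The case against.** The strongest reply is that Table 6 already covers the matter. It plans subgroup analyses of the ≥1 endpoint for the Section 7.5 variables, and Section 7.5 itself calls IND site status a subgroup. On that reading the correct analysis by site status is already in the plan. This carries weight. A reader might infer from SAP 7.5 that the plan would say nothing about whether the Step 3 result is consistent across site types, and Table 6 does not allow that inference. The reply does not settle the point, however. Section 7.5 introduces IND site status apart from its main list and attaches named outcomes to it, so the two places still disagree on the threshold.

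A reader might also infer that the response rate would be close to zero in both arms. The documents do not support that. The ceiling is the Class III share, and the number of Class III patients who would reach Class I is unknown. The plan also appears to expect a usable Class III group: baseline Class III is a planned subgroup level, and Step 6 is a confirmatory test in SRT-eligible patients, who must be in Class III or worse.

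A third reply is that this is an obvious slip, given how often ≥1 appears, and that a programmer would probably notice it. That is likely, but it is a reason to correct the text. Finally, the difference is one symbol, and converting a PDF to text can lose the bar under a ≥ sign. The ≥ sign does survive elsewhere in SAP 7.5, in the age and body mass index subgroups. If the signed PDF shows ≥1, the point closes.

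**Conclusion.** The point holds as an inconsistency in an operative analysis rule. SAP 7.5 uses >1 where the endpoint definition, Step 3 and Table 6 use ≥1. Taken literally, it makes every baseline Class II patient and every Class III to II improver a non-responder, and it caps the response rate at the baseline Class III share.

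The enumeration depends only on the scale and the entry criteria. The 10%, 25% and 50% ceilings are illustrations under assumed shares. That Step 3 was the intended endpoint is a strong inference from context; the SAP does not state it.

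The consequence is small. One subgroup analysis is affected, and SAP 7.1 assesses subgroup analyses at a nominal level without multiplicity adjustment. A reader might suppose that the confirmatory NYHA result is in doubt. It is not: Step 3 and Step 8 carry the correct threshold, and the primary analysis and type I error control do not depend on this item.

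**What to change.** In SAP 7.5, change >1 to ≥1 for the NYHA item and state that it is assessed at Week 24. Refer to SAP 7.8.1 item 3 for missing data: Week 20 is used when Week 24 is missing, and the patient is a non-responder when both are missing. Section 7.5 then agrees with Table 6 and with Step 3.

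If an improvement of two or more classes was really meant, define it as a separate exploratory endpoint and add the ≥1 analysis by IND site status beside it.

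The cost is one symbol and a short clause, made before database lock. No new data, sample size change or change to the testing hierarchy is needed.

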7.6. Multiple Comparisons and Multiplicity

The null hypothesis for the primary and secondary efficacy variables in the FAS will be tested in the pre-specified order using a closed testing procedure.

For preservation of the overall type I error rate at two-sided 0.05 for the primary and secondary endpoints, the closed testing procedure will be used to address multiplicity. The primary endpoint is tested first at two-sided 0.05. If the primary endpoint achieves statistical significance at two-sided alpha level of 0.05, then the secondary endpoints will be tested at two-sided 0.05, with their testing being in the sequential order of KCCQ-CSS change from baseline, proportion of patients with ≥ 1 NYHA functional class improvement, post-Valsalva LVOT-G change from baseline, and proportion of patients with post-Valsalva LVOT-G < 30 mmHg in FAS at Week 24; duration of SRT eligibility up to 24 weeks of treatment for those who were SRT eligible at baseline; KCCQ-CSS change from baseline, proportion of patients with ≥ 1 NYHA functional class improvement, post-Valsalva LVOT-G change from baseline, and proportion of patients with post-Valsalva LVOT-G < 30 mmHg in FAS at Week 12; and change from baseline to Week 24 in total workload. The testing steps are described as follows in [Table 4](#):

Table 4: Testing Steps

Step 1	The null hypothesis for the primary endpoint is that there is no treatment difference in the change from baseline to Week 24 in pVO ₂ between patients randomized to placebo and those randomized to aficamten in the FAS. The hypothesis will be tested at the two-sided significance level of 0.05. If this hypothesis is rejected, testing will proceed to Step 2; otherwise testing will stop.
Step 2	The null hypothesis for the first secondary endpoint is that there is no treatment difference in the change from baseline to Week 24 in KCCQ-CSS in the FAS. The hypotheses will be tested at the two-sided significance level of 0.05. If this hypothesis is rejected, testing will proceed to Step 3; otherwise testing will stop.
Step 3	The null hypothesis for the second secondary endpoint is that there is no treatment difference in proportion of patients with ≥ 1 NYHA functional class improvement at Week 24 in the FAS. The hypotheses will be tested at the two-sided significance level of 0.05. If this hypothesis is rejected, testing will proceed to Step 4; otherwise testing will stop.
Step 4	The null hypothesis for the third secondary endpoint is that there is no treatment difference in change from baseline to Week 24 in post-Valsalva LVOT-G in the FAS. The hypotheses will be tested at the two-sided significance level of 0.05. If this hypothesis is rejected, testing will proceed to Step 5; otherwise testing will stop.
Step 5	The null hypothesis for the fourth secondary endpoint is that there is no treatment difference in the proportion of patients with post-Valsalva LVOT-G < 30 mmHg at Week 24 in the FAS. The hypotheses will be tested at the two-sided significance level of 0.05. If this hypothesis is rejected, testing will proceed to Step 6; otherwise testing will stop.
Step 6	The null hypothesis for the fifth secondary endpoint is that there is no treatment difference in duration for SRT eligible during the 24-Week treatment period in patients who were SRT eligible at baseline in the FAS. The hypothesis will be tested at the two-sided significance level of 0.05. If this hypothesis is rejected, testing will proceed to Step 7; otherwise testing will stop.
Step 7	The null hypothesis for the sixth secondary endpoint is that there is no treatment difference in the change from baseline to Week 12 in KCCQ-CSS in the FAS. The hypothesis will be tested at the two-sided significance level of 0.05. If this hypothesis is rejected, testing will proceed to Step 8; otherwise testing will stop.
Step 8	The null hypothesis for the seventh secondary endpoint is that there is no treatment difference in proportion of patients with ≥ 1 NYHA functional class improvement at Week 12 in the FAS. The hypotheses will be tested at the two-sided significance level of 0.05. If this hypothesis is rejected, testing will proceed to Step 9; otherwise testing will stop.
Step 9	The null hypothesis for the eighth secondary endpoint is that there is no treatment difference in change from baseline to Week 12 in post-Valsalva LVOT-G in the FAS. The hypotheses will be tested at the two-sided significance level of 0.05. If this hypothesis is rejected, testing will proceed to Step 10; otherwise testing will stop.

Step 10	The null hypothesis for the ninth secondary endpoint is that there is no treatment difference in the proportion of patients with post-Valsalva LVOT-G < 30 mmHg at Week 12 in the FAS. The hypotheses will be tested at the two-sided significance level of 0.05. If this hypothesis is rejected, testing will proceed to Step 11; otherwise testing will stop.
Step 11	The null hypothesis for the tenth secondary endpoint is that there is no treatment difference in change from baseline to Week 24 in total workload in the FAS. The hypotheses will be tested at the two-sided significance level of 0.05.

7.7. Analysis of the Primary Efficacy Endpoint

7.7.1. Primary Efficacy Analysis

The primary endpoint is change in pVO₂ from baseline to Week 24. The **primary analysis** will be performed using an ANCOVA model that includes terms of treatment, randomization stratification factors (beta-blocker use status and CPET modality), baseline pVO₂ and baseline body weight as covariates in the FAS. [Table 5](#) below displays details of the two estimands for the primary endpoint.

Table 5: Estimands for Primary Endpoint

Attributes	Primary Estimand	Secondary Estimand
Population	FAS, target population of potentially treatable aficamten subjects.	Hypothetical target population of potentially treatable aficamten subjects continue with treatment and are capable of completing the Week 24 assessment. Subjects with missing Week 24 pVO ₂ due to intercurrent events or discontinuing treatment prior to Week 24 will be excluded.
Variable	Change from baseline to Week 24 in pVO ₂ . Data to be analyzed include all observed Week 24 pVO ₂ values from subjects who complete 24 weeks of treatment, or from subjects who early terminate from the treatment but remain in the study and have Week 24 pVO ₂ and imputed pVO ₂ for subjects who don't have Week 24 pVO ₂ . Imputation details are provided below.	Change from baseline to Week 24 in pVO ₂ . Data to be analyzed include observed pVO ₂ values from subjects who complete at least 24 weeks of treatment.
Measure of intervention effect	Mean treatment difference regardless of completing 24 weeks of treatment and experiencing intercurrent events.	Mean treatment difference among all subjects who remained on their randomized treatment for 24 weeks.

Subjects will be followed per the schedule of assessments from randomization through their final visit irrespective of whether the subject is continuing to receive study treatment. Reasons for not completing Week 24 CPET will be recorded on eCRF; categories of reasons include adverse

events, early termination, equipment failure, investigator decision, subject decision and other. The percentage of missing CPET data at Week 24 and the reasons for the missing data will be tabulated in the FAS. The following type of intercurrent events could preclude CPET at Week 24.

- Death
- Hospitalization
- CV AEs
- non-CV AEs (e.g., orthopedic injury)
- COVID-19 related intercurrent events e.g., subjects' decision to early terminate from the study due to the COVID-19 precautions, site closures, hospitalization due to COVID-19, or COVID-19 symptoms preventing subjects from coming to the Week 24 visit.

CPET data deemed to be invalid by the CPET core lab will be treated as missing CPET data in the analysis. CPET core lab flags the CPET results as invalid when there are:

- Technical equipment failure during CPET (i.e., air leak/lack of proper equipment utilization such as missing nose clip leading to lack of capture of gas exchange data)
- Transient non-cardiac issues that precluded conduct of the exercise study (as defined by inability to turn the pedals during the warm-up period for at least 3 min)
- CPET MOP-major CPET process deviation can impact one or more CPET variables.

Missing data as a result of an invalid assessment by the CPET core lab cab will be considered as missing at random.

Missing pVO₂ at Week 24 regardless of type of intercurrent events will be imputed using multiple imputation methodology under the MAR assumption for the primary analysis of the primary estimand. Missing Week 24 CPET is expected to be low. Patients will be followed according to the schedule of activities in the protocol from randomization through the date of final visit irrespective of whether the patient is continuing to receive IP unless the patient has discontinued prematurely from the study or withdrawn consent. The protocol allows up to 4 weeks extension of Week 24 in the event that the subject is temporarily unable to exercise due to an AE e.g., ankle sprain, upper respiratory infection etc. or due to equipment malfunction to ensure post randomization CPET data collection. Missing Week 24 CPET due to intercurrent events i.e., non-CV AEs or COVID-19 related intercurrent events can be considered as MAR. Death event is expected to be very rare given the patient population and the duration of the treatment in this study. Assume patients' risk of death event or hospitalization due to HCM symptom and other CV AEs is balanced between treatment groups, missing data due to this type of intercurrent events for the primary estimand will be imputed as MAR.

The imputation model will use regression multiple imputation which includes treatment group, randomization stratification factors, baseline pVO₂, sex, age, baseline hemoglobin, baseline body weight, baseline KCCQ CSS, and baseline NYHA class and the last available post randomization NYHA functional class, resting and Valsalva LVOT. Categorical variables, i.e., treatment group, baseline NYHA functional class, and sex will be specified in the CLASS statement. One hundred

(100) imputed datasets will be generated. Change from baseline in pVO₂ will be calculated based on the observed and imputed data. Each of the imputed dataset will be analyzed using the primary analysis ANCOVA model. LSM estimate of treatment difference and the standard error will be combined using Rubin's rules ([Rubin 1987](#)) to produce a LSM estimate of the treatment difference, its 95% confidence interval, and p-value for the test of null hypothesis of no treatment effect. LSM, LSM difference and the corresponding standard error, 95% CI and p-value will be presented.

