3.3. Sample Size Considerations

3.3.1. Sample Size Justifications

Assuming a difference in change from baseline in pVO₂ of 1.5 mL/kg/min for CK-3773274 compared to placebo, a standard deviation (SD) of 3.5 mL/kg/min, accounting for limiting beta-blocker use (less than ~70%), limiting exercise modality of bicycle (less than ~50%) and 10% of patients missing change from baseline data of the primary endpoint, a sample size of 270 patients at randomization ratio of 1:1 (approximately 135 randomized to CK-3773274 and 135 randomized to placebo) provides more than 90% power to detect the difference in pVO₂ change from baseline to Week 24 with a 2-sided type I error of 0.05.

During the study, Cytokinetics will periodically assess in a blinded fashion the aggregate pooled missing data rate and overall pooled SD for the change from baseline in pVO₂ at Week 24. If the pooled SD is larger than expected, Cytokinetics may consider increasing the sample size once in order to maintain the intended power.

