7.4. Planned Covariates

Baseline covariates include but are not limited to the stratification factors and baseline measurements. For CPET related endpoints, covariates age, sex, baseline weight will also be evaluated. See [Section 7.7.4](#) for details evaluating covariates effect in the primary endpoint.

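### The primary ANCOVA leaves out sex and age; prespecifying both would be a cheap and probably small efficiency gain, and the current model is valid without them

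*SAP*

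**What the plan says.** The primary model in SAP 7.7.1 is an "ANCOVA model that includes terms of treatment, randomization stratification factors (beta-blocker use status and CPET modality"), with baseline pVO2 and baseline body weight as the continuous covariates. Protocol 9.4.2, both synopses, SAP Table 6 and the sample code in SAP 11.5 give the same model. Total workload (Step 11 of the testing order) follows the same approach, with its own baseline value replacing baseline pVO2.

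Sex and age appear in four other places:

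- **SAP 7.4, planned covariates:** "For CPET related endpoints, covariates age, sex, baseline weight will also be evaluated". The section then refers to 7.7.4.
- **SAP 7.7.1, imputation of missing Week 24 pVO2:** besides treatment, stratification factors and baseline pVO2, the regression uses "sex, age, baseline hemoglobin, baseline body weight, baseline KCCQ CSS, and baseline NYHA class", and the last post-randomization NYHA class and gradients.
- **SAP 7.5 and 7.7.3, subgroups:** sex and age group (split at 65) each enter a version of the primary model together with a treatment interaction.
- **SAP 7.7.4, supportive analyses:** one model carries all the subgroup covariates and their treatment interactions. Another repeats the ANCOVA with covariates kept by stepwise selection at 0.05. Both use observed data only.

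**The concern.** SAP 7.4 groups age, sex and weight for CPET endpoints. Weight is a fixed term in the primary model. Age and sex are not, and no reason is given for the split.

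Baseline pVO2 need not absorb what sex and age carry. CPET is scheduled only at screening and Week 24, so baseline is normally a single test. If that test has measurement error, adjusting for it removes only part of the stable between-patient difference, and stable predictors of the true level keep some information. Analysing change does not alter this: with baseline in the model, change and the Week 24 value give the same treatment estimate and the same residual variance.

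The planned adjusted analyses cannot improve the primary test. The stepwise version chooses its covariates by looking at the outcome and leaves out patients with imputed values. What is at stake is some precision on the endpoint that gates all ten secondary tests, and on total workload.

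**Working it through.** **1. Reproduce the plan's power.** Inputs from SAP 3.3.1: a difference "of 1.5 mL/kg/min for CK-3773274 compared to placebo", "a standard deviation (SD) of 3.5 mL/kg/min", "270 patients at randomization ratio of 1:1", "10% of patients missing change from baseline data of the primary endpoint", and a test "with a 2-sided type I error of 0.05".

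- Evaluable per arm: 135 × 0.90 = 121.5.
- SE = 3.5 × √(2/121.5) = 0.449, and 1.5/0.449 = 3.34.
- Normal approximation: Φ(3.34 − 1.96) = 91.6%. Noncentral t: 91.4%.
- Cross-check: 90% power needs 115 per arm, 230 in total; 230/0.90 = 256, below 270.

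The claim of more than 90% holds.

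**2. Cost of two extra parameters.** The current model has six parameters and the extended one eight. With N = 243 evaluable, the variance factor is about 1 + 2/(243 − 9) = 1.0085, with 235 error degrees of freedom. If sex and age explain nothing further, power falls from 91.4% to 91.2%. Break-even is a partial R² of about 2/(243 − 6) = 0.008.

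**3. Possible gain.** The documents give neither the reliability of the baseline test nor the variance that sex and age explain, so both are assumptions here. Scale the pVO2 variance to 1. Let ρ be the reliability, and g the share of true variance explained by sex and age, both taken after the covariates already in the model.

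- Residual variance now: 1 − ρ².
- With sex and age: (1 − ρg) − [ρ(1 − g)]²/(1 − ρg).

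Example, ρ = 0.75 and g = 0.50: now 0.4375; with them 0.625 − 0.375²/0.625 = 0.400. The reduction is 1 − 0.400/0.4375 = 8.6%.

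Taking 3.5 as the residual SD under the current model, and charging the two parameters:

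| ρ | g | Fall in residual variance | Power | Change (points) |
|---|---|---|---|---|
| 0.75 | 0.05 | 0.6% | 91.3% | −0.1 |
| 0.75 | 0.20 | 2.5% | 91.9% | +0.4 |
| 0.75 | 0.50 | 8.6% | 93.4% | +2.0 |
| 0.85 | 0.05 | 0.4% | 91.3% | −0.1 |
| 0.85 | 0.20 | 1.7% | 91.6% | +0.2 |
| 0.85 | 0.50 | 6.0% | 92.7% | +1.3 |
| 0.90 | 0.05 | 0.3% | 91.3% | −0.2 |
| 0.90 | 0.20 | 1.2% | 91.5% | +0.1 |
| 0.90 | 0.50 | 4.3% | 92.3% | +0.9 |

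Before the parameter cost, the top of the range is worth 270/(1 − 0.0857) − 270 ≈ 25 patients, and the bottom less than one.

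**4. If 3.5 is the unadjusted SD of change.** The plan does not say which it is. Under the same error model the variance of change is 2(1 − ρ), so the current ANCOVA already reduces it by the factor (1 − ρ²)/[2(1 − ρ)] = (1 + ρ)/2. For ρ = 0.75, 0.85 and 0.90 the current power is then 94.5%, 93.3% and 92.7%. The net change from adding sex and age runs from about −0.2 points (ρ = 0.90, g = 0.05) to +1.5 (ρ = 0.75, g = 0.50).

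**The case against.** The strongest reply is that nothing here is an error. The model is prespecified, is the same in both documents, adjusts for both stratification factors, baseline pVO2 and weight, and meets its power target. That stands.

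A reader might go further than the documents allow in three ways:

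- **That the imputation model proves precision is being lost.** It does not. Imputation models are commonly richer than analysis models, to make missing at random more plausible. This one also holds hemoglobin, KCCQ-CSS and NYHA class, and the same argument would bring those in. The case for sex and age rests instead on SAP 7.4 grouping them with weight, and on their being baseline facts recorded at screening.
- **That the plan overlooks sex and age.** It does not. SAP 7.4 says only that they will be evaluated, and 7.5, 7.7.3 and 7.7.4 do so.
- **That the gain is free and certain.** It costs two parameters, and the partial R² is unknown. Weight is probably correlated with sex, so the low values of g deserve weight. The error model also assumes that patients do not truly differ in their change over 24 weeks. With individually titrated dosing they may, and that would shrink the proportional gain.

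What survives is that fixed, prespecified covariates are a better route than stepwise selection, and that the possible loss is very small.

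**Conclusion.** This is an optional efficiency improvement. The omission causes no bias and no type I error inflation, and power exceeds 90% with or without the change under every assumption shown.

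The size cannot be fixed from the documents. Over reliability 0.75 to 0.90 and 5% to 50% of true variance explained beyond the existing covariates, residual variance falls by about 0.3% to 9%, and power moves by about −0.2 to +2.0 points net of two parameters. The worst case, where sex and age add nothing, costs about 0.2 points. The upper end needs both low reliability and a large explained share. No separate figure can be given for total workload, and the pVO2 range should not be carried over to it.

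**What to change.** Add sex and age (continuous) as fixed covariates to the primary ANCOVA in SAP 7.7.1, Table 6 and the 11.5 code, and to the total workload ANCOVA. Align Protocol 9.4.2 and both synopses. Make the change before unblinding, which SAP 4.2 places after database lock. Keep the current model as a prespecified sensitivity analysis, and leave stepwise selection as supportive only.

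The imputation model for pVO2 already contains both variables and needs no change. The text should say whether the analyses that inherit the primary model follow it: subgroups (7.7.3), the secondary estimand (7.7.4), and exploratory CPET and CMR measures (7.9.1). It should also say how the sex and age-group subgroup models avoid entering the same variable twice.

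The cost is a coordinated edit to both documents and the code, two degrees of freedom, and no new data. If the sponsor prefers the current model, a sentence in SAP 7.4 should explain why weight is adjusted for and age and sex are not.
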